# 5.0 Treatment Plan (see Appendix D)

All patients will start with R-FND.

5.1 R-FND

5.1.1 Initial Dose Regimen of R-FND - Course 1: please note that there are 2 doses of rituximab for course 1 only:

AGENT	DOSE	DAY	ROUTE	TIME
Fludarabine	25 mg/m²/day	2-4	I.V.	5-30 minutes
Mitoxantrone	10 mg/m 	2	I.V.	5-30 minutes
Dexamethasone	20 mg/day	2-6	PO or I.V.	
Rituximab*	375 mg/m²/dose	1* & 8	I.V.	4-6 hours

\*For leukemic patients, because of the risk of lysis, rituximab Day 1 dose will be deferred to Day 3 (or later at clinician's discretion). Missed rituximab doses will be made up in subsequent courses; discuss with P.I.

Subsequent Monthly Dose Regimen of R-FND – Courses 2 and beyond: please note that there is only 1 dose of rituximab:

AGENT	DOSE	DAY	ROUTE	TIME
Fludarabine	25 mg/m²/day	1-3	I.V.	5-30 minutes
Mitoxantrone	10 mg/m 	1	I.V.	5-30 minutes
Dexamethasone	20 mg/day	1-5	PO or I.V.	
Rituximab	375 mg/m 	1	I.V.	4-6 hours

5.1.2 Rituximab is recommended to start two hours before fludarabine. Mitoxantrone is recommended to be given after the first dose of fludarabine. Courses are recommended to be repeated each four weeks, after documentation of recovery from the prior course, including platelets > 100,000, and granulocytes > 1500.

5.1.3 Dose Levels

	-2	-1	0
Fludarabine	16 x 3	20 x 3	25 x 3
Mitoxantrone	6	8	10

Dose Reduction of rituximab is discouraged, but may be discussed with the P.I.

5.1.4 Patients are recommended to receive fludarabine phosphate I.V. over 5-30 minutes daily for 3 days. Mitoxantrone is recommended to be given I.V. over 5-30 minutes. Rituximab will be given as in section 5.1. Courses are recommended to be repeated every 4 weeks. Restaging on R-FND is recommended to be conducted after completion of 2 and 4 courses.

5.1.5 Patients achieving a stable partial response or demonstrating continued response after 4 courses may be given an additional 2 courses. Discuss with P.I.

5.1.6 Patients demonstrating progressive disease or no response after 2-4 courses will come off study. See section 9.1.

5.1.7 Dose adjustment to the next lower level will be made if pneumonia, septicemia, or other life-threatening infection occurs with any course. If recovery of the WBC or platelet count to the level prior to treatment exceeds 35 days, the dose may be decreased 1 level. If grade 3 or 4 toxicities to other organ systems develops, the dose level may be lowered 1 or 2 levels respectively.

5.1.8 Four courses is the intended limit for R-FND. For patients with substantial (>20%) ongoing shrinkage of measurable disease between courses 2 and 4 will receive additional R-FND, if their hematologic tolerance has been good. If such special circumstances warrant consideration of additional R-FND, please discuss with P.I.

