5.6. Chemotherapy Dose Modification Guidelines

5.6.1 Recommended Guidelines for Hematological Toxicity: for fludarabine and mitoxantrone (see 5.1.3):

Lowest granulocytes	Lowest Platelets	Modification		
>200	> 20,000	No change		
<200 for > 5 days and/or	< 20,000	Decrease one level		
documented infection with neutropenia	Bleeding	Decrease one level		

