5.6.2 For all other toxicities (see Appendix B)

G	ra	de	
			-

- 0-2 No change
- 3 Decrease one level
- 4 Stop Treatment
- 5.6.3 Duration of therapy and intervals between courses:
- a) R-FND courses are recommended to repeated every 28 days, after verification of hematologic recovery.

b) Total length of R-FND treatment will be 4 courses for most patients. Exceptions should be discussed with PI, e.g. give more if response is slow (see sections 5.1.5 and 5.1.8), or stop early if there is evidence of cumulative myelosuppression, with more than 6 weeks before recovery of granulocytes to 1000 or more or platelets to 100,000 or more.

5.6.4 Patients older than 60 years will receive full doses of chemotherapy.

5.6.5 Anyone experiencing delayed recovery of granulocyte counts (>35 days) or neutropenic fever will be candidates for colony stimulating factor support, with the chemotherapy doses adjusted down one dose level.

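### After a grade 4 non-hematologic toxicity during R-FND, section 5.1.7 permits continuing two dose levels down, while section 5.6.2 says to stop treatment

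*Combined protocol and SAP*

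**What the plan says.** Section 5.1 sets out R-FND dosing. The table in 5.1.3 has three levels for fludarabine and mitoxantrone: 0, -1 and -2. Section 5.1.7 then says when to move down them. Its last sentence concerns organ toxicity: "If grade 3 or 4 toxicities to other organ systems develops, the dose level may be lowered 1 or 2 levels respectively".

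Section 5.6 returns to chemotherapy dose modification. Section 5.6.1 covers hematologic toxicity for fludarabine and mitoxantrone and refers back to 5.1.3. Section 5.6.2 covers all remaining toxicities by grade. Grades 0 to 2 need no change; the next two rows are "3 Decrease one level" and "4 Stop Treatment".

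**The concern.** The same clinical event leads to two different actions. A physician who follows 5.1.7 may give another course at level -2. A physician who follows 5.6.2 gives none. Both can point to the protocol, and anyone checking compliance could not say whether the further course was a deviation.

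What is at stake is patient safety: whether someone is re-exposed to fludarabine and mitoxantrone after an organ toxicity of the highest grade on the 0-4 scale described in section 8.3. It is also a matter of consistent treatment, since two patients with the same event could be handled in opposite ways.

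**Working it through.** The plan states no figure on this point that could be reproduced. The check is a comparison of text, plus the size of the dose that is in question.

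**Step 1: do the two rules cover the same decision?** Section 5.1.7 is part of the R-FND dosing section and refers to dose levels, which 5.1.3 defines for fludarabine and mitoxantrone only. Section 5.6 concerns chemotherapy dose changes. Since 5.6.1 takes the hematologic toxicities for those two drugs, 5.6.2 is the non-hematologic remainder. Phase, drugs and class of toxicity therefore match.

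**Step 2: compare by grade.**

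| Grade, non-hematologic | 5.1.7 | 5.6.2 | Same? |
|---|---|---|---|
| 3 | may go down 1 level | go down 1 level | yes |
| 4 | may go down 2 levels and continue | stop | no |

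The match at grade 3 supports the view that both sections address one decision. In 5.1.7, the word *respectively* ties grade 4 to the two-level step.

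**Step 3: does any other supplied text settle it?**

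- 5.6.3(b) sends exceptions on the number of courses to the PI. Its example of stopping early is cumulative myelosuppression, not organ toxicity.
- 7.9.4 requires approval of dose changes, but under the heading on outside physicians. The approving physician would still face two rules.
- 8.4 and 11.4 require prompt reporting of serious events. They give no dose rule.
- 9.4 lists unacceptable toxicity as a reason for removal from study, without naming a grade.
- 11.3 makes the Study Chairman the arbiter of disagreements over response and toxicity. It does not say which dose rule applies.

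None gives either section precedence. Appendices B, D and N were not available to check. Section 8.3 describes Appendix B as the grading system. Appendix D is cited for the treatment plan and Appendix N for the chemotherapy instructions sent to outside physicians. Even if D or N repeats one of the rules, the body text still disagrees with itself.

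**Step 4: the dose in question, for a patient at level 0.** The inputs are the 5.1.3 table, with units from 5.1.1.

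- Fludarabine per course: level 0 is 25 x 3 = 75 mg/m2; level -2 is 16 x 3 = 48 mg/m2; 48/75 = 0.64.
- Mitoxantrone per course: level 0 is 10 mg/m2; level -2 is 6 mg/m2; 6/10 = 0.60.

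Under 5.1.7 each further course could therefore carry 64% and 60% of the full doses. Under 5.6.2, with the stop read as permanent, there is no further course.

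**The case against.** The strongest reply is that the conflict is soft. Section 5.1.7 says *may*, section 5.6 is headed as guidelines, and stopping satisfies both texts. On this view the grade-by-grade list in 5.6.2 is the specific rule and simply governs the permissive sentence. The first part stands: a reader might infer that the protocol orders re-treatment after grade 4, and it does not. But an express permission to continue in one section and a stop in another still disagree, and no text says that 5.6.2 prevails.

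A second reply is that 5.6.2 does not define the stop as permanent. If it meant only the current course, a later restart two levels down would satisfy both sections. This is fair, and permanence is an assumption here. It is the natural reading, because the row follows directly after a dose reduction at grade 3 and says nothing about resuming.

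A third reply is that grade 4 events reach the PI and the Study Chairman under 8.4 and 11.4, so a lone clinician is unlikely to decide. This lowers the risk of inconsistent handling but leaves the person who decides with two rules.

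Two extensions of the point should not be drawn:

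- A reader might infer a similar clash for life-threatening infection. Section 5.1.7 has its own instruction for that event, "Dose adjustment to the next lower level will be made if pneumonia, septicemia, or other life-threatening infection occurs with any course", and a residual row for other toxicities need not displace it.
- A reader might treat the lack of any level below -2 as a further conflict. Where no lower level exists, 5.1.7 offers no dose to continue on, so nothing competes with the stop in 5.6.2.

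**Conclusion.** The point holds as an internal contradiction limited to grade 4 non-hematologic toxicity during R-FND. For a patient at level 0, the two rules differ between further courses at 64% of the fludarabine dose and 60% of the mitoxantrone dose, and no further R-FND. It rests on two assumptions: that the stop in 5.6.2 is permanent, and that it refers to R-FND, as the heading of 5.6 suggests.

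The frequency is unknown, because the documents give no rate of such events on R-FND. Nor can a total excess exposure be fixed: 5.1.8 says "Four courses is the intended limit for R-FND", but 5.1.5 and 5.1.8 both provide for additional courses in some patients.

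A reader might infer that the contradiction undermines the primary result. The documents do not support that. Section 10.3 includes every patient who received any chemotherapy, and neither the sample size in 10.1 nor the stopping rule in 10.5 uses the dose-modification rules. A reader might also infer that stopping early bars a patient from Zevalin, since 5.4.1 refers to four courses. That is uncertain, because 5.6.3(b) allows exceptions after discussion with the PI.

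This should be fixed because it concerns patient safety and is easy to correct. It is not a threat to the trial's analysis.

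**What to change.** Replace the last sentence of 5.1.7 with a rule such as: *For non-hematologic toxicity, grade 3: lower 1 level; grade 4: stop R-FND (see 5.6.2).* This lets the stricter of the two existing rules govern. If Appendix D or Appendix N carries a dose rule, make it match.

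The documents do not show which rule the sponsor intended. Choosing the stricter one is a safety judgement; the essential thing is that one grade 4 rule remains.

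The change costs one amended sentence and a check of two appendices. Its downside is that a few patients lose the option of reduced-dose R-FND after a grade 4 organ toxicity. Sample size, monitoring, enrolment and analysis stay as they are.

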## 5.2 GUIDELINES FOR RITUXIMAB ADMINISTRATION: CAUTION: DO NOT ADMINISTER RITUXIMAB AS AN INTRAVENOUS PUSH OR BOLUS

Recommended: Premedication (two tablets [375mg or 500 mg] of acetaminophen orally and 25 to 100 mg diphenhydramine 5.2.1 hydrochloride orally or intravenously) to be administered 30 to 60 minutes prior to starting each infusion of rituximab.

5.2.2 The drug may be administered via a peripheral or central intravenous line.

Recommended: During the rituximab infusion, the patient's vital signs (blood pressure, pulse, respiration, temperature) are 5.2.3 recommended to be monitored every 15 minutes x 4 or until stable and then hourly until the infusion is discontinued. Available at the bedside prior to rituximab administration it is recommended to have epinephrine for subcutaneous injection, diphenhydramine hydrochloride for intravenous injection, and resuscitation equipment for emergency management of anaphylactoid reactions.

Recommended: The initial dose rate at the time of the first rituximab infusion is recommended to be 50 mg/hr for the first half hour. If 5.2.4 no toxicity is seen, the dose rate may be escalated gradually (50 mg/hour increments at 30-minute intervals) to a maximum of 500 mg/hr. If the first dose of rituximab is well tolerated, the starting flow rate for the administration of doses 2-4 will be 100 mg/hour then increased gradually (100 mg/hour increments at 30-minute intervals) not to exceed 600 mg/hr.

Patients may experience transient fever and rigors with infusion of chimeric anti-CD20 (rituximab) antibody. When these side effects 5.2.5 are noted, the antibody infusion is recommended be slowed or interrupted. The patient should be observed and the severity of the side effects should be evaluated. The patient should be treated according to the best available local practices and procedures. Following observation, when the patient's symptoms improve, the infusion may be resumed, initially at half the previous rate (see table below). Upon resolution of all side effects and in the judgement of the investigator, the patient's dose may be gradually escalated (50 mg/hr increments at 30 minute intervals) to a maximum rate of 300 mg/hr. Following the antibody infusion, it is recommended that the IV line be kept open for medications, as needed. If complications occur during the rituximab infusion, the patient should be observed for two hours after the completion of the infusion.

			Mucosal						
			Congestion/		% Drop in				
Dose Rate	Fever o	r Rigors or	Edema	or	Systolic BP	,			
Decrease to 1/2	>38.5°C	Mild/Moderate	Mild/Moderate		>30 mm Hg				

Since transient hypotension has been reported during rituximab infusions, consideration should be given to withholding anti-5.2.6 hypertensive medications the day of the rituximab infusion.

5.3 Antibiotic prophylaxis

5.3.1 Prophylaxis for pneumocystis carinii

5.3.1.1 All patients are recommended to receive prophylaxis with trimethoprim-sulfa (TMP-SMX) as follows: 2 DS tablets twice daily, on Sat. & Sun.

5.3.1.2 For TMP-SMX allergy, patients are recommended to receive pentamidine aerosol therapy: 300 mg q 4 wks using a Respigard II nebulizer.

5.3.1.3 For any problems, please consult P.I. and/or Infectious Disease

#### 5.3.2 Viral prophylaxis

Valacyclovir 500 mg po qd x 10d, days 8-17 of each cycle, is recommended. 5.3.2.1

5.4 Zevalin Radioimmunotherapy (see Appendices I and J)

Candidate patients: PR or CR after R-FND x 4 5.4.1

5.4.2 Exclusions:

- persistent marrow infiltrate > 25% -- n.b., most such patients will not meet PR criteria anyway. ٠
- Hypocellular bone marrow (cellularity less than 15%) •
- Marked reduction in bone marrow precursors of one or more cell lines (granulocytic, megakaryocytic, erythroid)
- Platelet count <100.000/mm^3 ٠
- creatinine, bilirubin, AST/ALT or alkaline phosphatase > 2 x the upper limit of normal.
- Active infection
- pleural effusion

- G-CSF or GM-CSF within 2 weeks
- Performance status 3 or more

5.4.3 Schedule: Zevalin to start approximately 12-16 weeks after last course of R-FND, pending hematologic recovery as outlined above in 5.4.2

5.4.3.1 The Y isotope order form must be completed and faxed to the designated isotope vendor preceding the initial rituximab infusion. Patients will receive an initial infusion of 250 mg/m^2 rituximab. One week later, patients must receive a second infusion of 250 mg/m^2 of rituximab and 0.3 mCi/kg of ZEVALIN. The exact dose of ZEVALIN will be based on the patient's weight during the baseline evaluation. The maximum dose is not to exceed 32 mCi of Y.

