## 2.4 Rituximab and other monoclonal antibodies

Rituximab is a chimeric anti-CD20 monoclonal antibody (25). As a single agent, it has been effective and well tolerated (26-28). In combination with chemotherapy, it has been well tolerated (24,29). Ongoing trials suggest that rituximab can add to the impact of chemotherapy (30). Rituximab is capable of inducing molecular remissions (31).

Zevalin is a radioimmunoconjugate that targets CD20, the same pan B antigen recognized by rituximab. It is a highly active single agent (32, 33).

The safety profile of Zevalin in five clinical trials revealed that AEs are primarily hematologic with Grade 4 neutropenia, thrombocytopenia, and anemia occurring in 30%, 10%, and 4% of patients, respectively. Most nonhematologic AEs were Grade 1 or 2 and the incidence was comparable to that seen with rituximab. Hematologic toxicity did not correlate with any of the dosimetric or pharmacokinetic parameters analyzed. Patients were effectively screened for safe treatment using clinical selection criteria including percent bone marrow involvement with NHL (<25%), baseline platelet count (> 100,000 cells/mm^3). Patients were treated safely using individualized dosing based on patient weight and platelet count. The incorporation of Zevalin, in sequence with chemotherapy, in the front-line strategy proposed in this protocol is investigational.

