# 3.0 Background Drug Information

3.1 Fludarabine is commercially available.

3.2 Mitoxantrone is commercially available.

3.3 Dexamethasone is commercially available.

3.4 Rituximab (Rituxan®) is commercially available. Safety information is as follows:

Hematologic Events: In clinical trials, Grade 3 and 4 cytopenias were reported in 48% of patients treated with rituximab; these include: lymphopenia (40%), neutropenia (6%), leukopenia (4%), anemia (3%), and thrombocytopenia (2%). The median duration of lymphopenia was 14 days (range, 1 to 588 days) and of neutropenia was 13 days (range, 2 to 116 days). A single occurrence of transient aplastic anemia (pure red cell aplasia) and two occurrences of hemolytic anemia following rituximab therapy were reported.

In addition, there have been a limited number of post-marketing reports of prolonged pancytopenia, marrow hypoplasia, and late onset n (defined as occurring 40 days after the last dose of rituximab) in patients with hematologic malignancies. In reported cases of late onset neutropenia (NCI-CTC Grade 3 and 4), the median duration of neutropenia was 10 days (range 3 to 148 days). Documented resolution of the neutropenia was described in approximately one-half of the reported cases; of those with documented recovery, approximately half received growth factor support. In the remaining cases, information on resolution was not provided. More than half of the reported cases of delayed onset neutropenia occurred in patients who had undergone a prior autologous bone marrow transplantation. In an adequately designed, controlled, clinical trial, the reported incidence of NCI-CTC Grade 3 and 4 neutropenia was higher in patients receiving rituximab in combination with fludarabine as compared to those receiving fludarabine alone (76% [39/51] vs.39% [21/53]).

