3.4.4 Reconstitution and dilution of rituximab

Using a sterile syringe and a 21 gauge or larger needle, transfer the necessary amount of rituximab from the vial into a partially filled IV pack containing sterile, pyrogen-free 0.9% Sodium Chloride, USP (saline solution). The final concentration of rituximab should be 1 mg/mL. Mix by inverting the bag gently.

Caution should be taken during the preparation of the drug. Parenteral drug products should be inspected visually for particulate matter prior to administration. Preparations of rituximab containing visible particles should not be used. As with all parenteral drug products, aseptic procedures should be used during the preparation and administration of rituximab.

NOTE: DO NOT USE A VACUUM APPARATUS to transfer rituximab from the syringe to the infusion pack. DO NOT USE evacuated glass containers which require vented administration sets, because this causes foaming when air bubbles pass through the solution.

3.5 Zevalin: Zevalin is composed of the following: a murine IgG1 kappa monoclonal antibody IDEC-2B8 (ibritumomab); the linker chelator tiuxetan (isothiocyanatobenzyl MX-DTPA); and the radioisotope Y that is securely chelated via the linker. Like its unlabeled chimeric counterpart, rituximab, Zevalin targets the CD20 antigen present on 95% of B cell lymphomas. IDEC-In2B8 is the Indium-labeled murine monoclonal antibody used for imaging and dosimetry. Rituximab is given initially to clear peripheral B lymphocytes and optimize biodistribution of the radiolabeled antibody. Dosimetry studies have shown that normal organ and red marrow radiation doses were estimated to be well under 2000 cGy and 300 cGy, respectively. Estimated median tumor absorbed dose as determined by data from 18 tumors in 9 patients was 1712 cGy (range 575 – 6710). In a specific analysis of safety, estimated absorbed red marrow radiation dose (performed by blood-derived and sacral image-derived methods), blood T1/2, blood AUC, plasma T1/2, and plasma AUC did not predict severity of hematologic toxicity as demonstrated by the lack of clear correlation between these variables. In a multicenter phase II trial, adverse events were primarily hematologic, transient, and reversible. The median nadirs were 34,000/mm^3 for platelets, 60/mm^3 for ANC, and 10.0 g/dL for hemoglobin. Grade 4 neutropenia and thrombocytopenia occurred in 31% and 12% of patients.

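### The recovery rule for starting Zevalin (5.4.3, defined by 5.4.2) sets a platelet limit but no neutrophil minimum

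*Combined protocol and SAP*

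**What the plan says.** Section 5.4.3 sets the timing and the condition for Zevalin in one sentence: "Zevalin to start approximately 12-16 weeks after last course of R-FND, pending hematologic recovery as outlined above in 5.4.2". What counts as recovery is therefore whatever 5.4.2 lists.

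That list excludes patients with residual marrow involvement above 25%, marrow cellularity under 15%, platelets under 100,000/mm3, liver or renal chemistry above twice the upper limit of normal, active infection, pleural effusion, growth factor in the previous 2 weeks, or performance status 3 or worse. One further item touches the granulocytic line, but in the marrow and without a number: "Marked reduction in bone marrow precursors of one or more cell lines (granulocytic, megakaryocytic, erythroid".

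For repeating R-FND, 5.1.2 recommends waiting until "after documentation of recovery from the prior course, including platelets > 100,000, and granulocytes > 1500".

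On toxicity after Zevalin, 2.4 reports "Grade 4 neutropenia, thrombocytopenia, and anemia occurring in 30%, 10%, and 4% of patients, respectively", and 3.5 reports, from a multicenter phase II trial, "Grade 4 neutropenia and thrombocytopenia occurred in 31% and 12% of patients". Section 2.4 adds: "The incorporation of Zevalin, in sequence with chemotherapy, in the front-line strategy proposed in this protocol is investigational".

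**The concern.** The cross-reference promises a definition of haematologic recovery, but the definition contains no granulocyte value. A responder who has a low ANC, adequate marrow, platelets of at least 100,000, no active infection and no recent growth factor passes every haematologic item in 5.4.2. That patient may then receive up to 32 mCi of 90Y (5.4.3.1), a single myelosuppressive dose that cannot be withdrawn once given.

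The protocol's other safeguards act only after the dose: weekly counts for 12 weeks (7.7), the hold at 2 treatment-related deaths (10.2) and the safety review after the first 10 patients complete Zevalin (10.4). Maintenance rituximab also goes ahead on schedule if counts are slow to recover after Zevalin (5.5.2). The decision to dose is therefore where a written ANC rule would help.

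**Working it through.** The plan states no figure on this point, so the check compares the rules and then looks at the timing.

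**Step 1. Count limits at each decision point.**

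| Decision | Section | Granulocytes | Platelets |
|---|---|---|---|
| Study entry | 4.10.2 | 1,000 | 100,000 |
| Repeat an R-FND course | 5.1.2 | above 1500 | above 100,000 |
| Stop R-FND early for slow recovery | 5.6.3 | 1000 | 100,000 |
| Give Zevalin | 5.4.2, through 5.4.3 | none | 100,000 |

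The platelet value is the same in all four rows. Zevalin is the only row without a granulocyte value.

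**Step 2. Test the 5.4.2 list on one patient.** Take a responder at the Zevalin visit with an ANC below 1,000, which neither 5.1.2 nor 5.6.3 would count as recovered, and with platelets of at least 100,000.

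- Marrow involvement and cellularity: passed if the marrow is adequate.
- Marrow precursors: passed unless the reduction is judged marked. The item describes the marrow, not the circulating count.
- Platelets: passed.
- Active infection: passed if there is none.
- Growth factor: passed if none was given in the last 2 weeks.

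No remaining item concerns blood counts, so the written rule allows the dose.

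**Step 3. Is the ANC known in time?** The re-evaluation after four courses includes a differential (7.2.1), and 7.1 recommends differentials during treatment. The list specific to the period before Zevalin (7.2.3) requires a CBC but does not mention a differential. The blood is drawn in any case, but no rule acts on the ANC.

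**Step 4. How likely is a low ANC so late?** Section 5.6.5 foresees granulocyte recovery beyond 35 days. Section 3.4 describes late-onset neutropenia after rituximab, "defined as occurring 40 days after the last dose of rituximab", in which "the median duration of neutropenia was 10 days (range 3 to 148 days".

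- Last R-FND rituximab to Zevalin, counted from day 1 of the last course: 12 × 7 = 84 to 16 × 7 = 112 days.
- Counted from the end of a 28-day course: 84 + 28 = 112 to 112 + 28 = 140 days.
- Duration needed for an episode that starts on day 40: 84 − 40 = 44 days at the shortest and 140 − 40 = 100 days at the longest.

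Both durations lie inside the reported 3-148 days but far above the 10-day median. A later onset would need a shorter episode; the documents give no distribution of onset times. The route is possible but remote.

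**The case against.** The strongest defence is that the gate was chosen on evidence. Section 2.4 says that patients in the earlier Zevalin trials were screened effectively with criteria that included marrow involvement and platelets. Section 5.4.2 keeps both and adds cellularity, marrow precursors, infection and growth-factor items. Together with a 12-16 week gap, these give substantial protection, and that part of the defence stands. It is not complete: the list in 2.4 is presented as partial, and the same section calls the sequence with chemotherapy investigational.

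The 5.1.2 value is a recommendation for repeating chemotherapy every 4 weeks, not a validated threshold for radioimmunotherapy. That also stands. It shows what this protocol regards as recovery, but the exact floor is a clinical choice.

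The late-onset reports are limited in number, and more than half were in patients with a prior autologous transplant, whereas this trial enrols previously untreated patients. That stands too, and is why few patients are likely to be affected.

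Appendices I and J, to which the 5.4 heading refers, are not in the text available and might hold an ANC limit. However, 5.4.3 names 5.4.2 as the definition.

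A reader might go further and infer from the toxicity rates that the gate guards the wrong count, since grade 4 neutropenia is 30/10 = 3.0 times (2.4) or 31/12 = 2.6 times (3.5) as frequent as grade 4 thrombocytopenia. The documents do not support that. These are rates after dosing, and nothing in the documents links the ANC before Zevalin to the depth, duration or complications of neutropenia afterwards. They make neutrophils relevant to the decision; they do not show that a floor would lower toxicity.

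**Conclusion.** The gap is real but small. The written start rule would let a patient with a low ANC, adequate marrow and adequate platelets receive Zevalin, although the protocol includes granulocytes when it defines recovery for R-FND. The conclusion rests on two points: 5.4.3 refers to 5.4.2 alone, and platelets are the only peripheral count limited there.

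No size in patients can be given. The documents do not report how often a low ANC occurs with platelets of at least 100,000 at this stage, so a reader should not infer that a material share of the 50 patients would be dosed while neutropenic. The existing exclusions and the time gap suggest few. Nor should a reader infer any effect on the trial's inference: neither TTP nor the stopping criterion in 10.5 depends on blood counts.

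This is a minor patient-safety improvement, worth making because it is cheap and the dose is irreversible.

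**What to change.** Add one exclusion to 5.4.2: *ANC < 1,500/mm3*. This takes its value from 5.1.2. If fewer delays are preferred, 1,000, as in 5.6.3, is an acceptable lower floor; the choice between them is clinical. In 7.2.3, write *CBC with differential* so that the ANC is available when the decision is made. If an appendix already holds an ANC limit, cite it in 5.4.2 instead.

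The cost is one line in 5.4.2 and two words in 7.2.3, with no additional blood draw. The downside is that a few patients will start Zevalin later or not at all; a floor of 1,000 would delay fewer than 1,500. The sample size, the TTP analysis and the monitoring program need no change.
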